### **8.7.3 Hypothesis Testing Strategy**

The efficacy of CR845 0.5 mcg/kg compared to placebo in pivotal Phase 3 study CLIN3103 will be evaluated based on 1 primary and 7 secondary efficacy endpoints.

Testing of the primary efficacy endpoint will be 2-sided and conducted at the 5% error level. The study will be considered positive if the null hypothesis of no treatment difference in the primary efficacy analysis of the primary endpoint (proportion of patients achieving  $\geq 3$ -point improvement from baseline with respect to the Worst Itching Intensity NRS) is rejected in favor of the alternative that patients randomized to CR845 experience significantly less itching compared to patients randomized to placebo.

To protect the Type 1 error, a gate-keeping strategy will be implemented. Although the p values corresponding to the hypothesis testing of the secondary variables will be reported, they will only be considered inferential if the primary analysis is statistically significant. Testing of the secondary efficacy endpoints will be performed sequentially at a 2-sided 5% error level in the order specified below. If the test of an endpoint in the sequence is not statistically significant, the p-value for the tests corresponding to the remaining endpoints in the sequence will not be considered inferential and the null hypotheses for the subsequent tests will not be rejected.

- Proportion of patients achieving  $\geq 4$ -point improvement from baseline with respect to the weekly mean of the daily 24-hour Worst Itching Intensity NRS at Week 12 of the Double-blind Treatment Period;
- Proportion of patients achieving  $\geq 3$ -point improvement from baseline with respect to the weekly mean of the daily 24-hour Worst Itching Intensity NRS at Week 8 of the Double-blind Treatment Period;
- Proportion of patients achieving  $\geq 3$ -point improvement from baseline with respect to the weekly mean of the daily 24-hour Worst Itching Intensity NRS at Week 4 of the Double-blind Treatment Period;
- Proportion of patients achieving  $\geq 4$ -point improvement from baseline with respect to the weekly mean of the daily 24-hour Worst Itching Intensity NRS at Week 8 of the Double-blind Treatment Period;
- Proportion of patients achieving  $\geq 4$ -point improvement from baseline with respect to the weekly mean of the daily 24-hour Worst Itching Intensity NRS at Week 4 of the Double-blind Treatment Period;
- Change from baseline in Skindex-10 Scale total score at Week 12 of the Double-blind Treatment Period;
- Change from baseline in 5-D Itch Scale total score at Week 12 of the Double-blind Treatment Period.

#### **8.7.4 Additional Efficacy Endpoints**

##### **8.7.4.1 Itch-intensity Measures**

- Proportion of patients who have an improvement from baseline at Week 12 of the Double-blind period with respect to the weekly mean of the 24-hour Worst Itching Intensity NRS scores  $\geq 1$  and  $\geq 2$ . The calculation of the proportions will be based on the NRS data using a multiple imputation (MI) approach for the missing data as in the primary efficacy analysis. A figure presenting the proportion of patients who have an improvement from baseline in NRS scores at Week 12 that is  $\geq 1$ ,  $\geq 2$ ,  $\geq 3$ , and  $\geq 4$  will be prepared.
- Change from baseline in the weekly mean of the 24-hour Worst Itching Intensity NRS score at each week of the Double-blind Treatment Period (Week 1 to

Week 12). Treatment differences between CR845 and placebo at each postbaseline time point will be evaluated using the same MMRM detailed in [Section 8.7.2](#).

- Proportion of patients who rate their itch condition as “Very much improved” or “Much Improved” at the end of Week 12 of the Double-blind Treatment Period/end of double-blind treatment, as measured by the Patient Global Impression of Change. Treatment difference will be tested using the Cochran-Mantel-Haenszel test, adjusting for strata. An exact test, such as the Fisher’s Exact Test, may be used if the observed count in a particular cell is small (ie, <5).

#### **8.7.4.2 Itch-related Quality-of-Life Measures**

Itch-related quality-of-life measures and their analyses will include:

- Change from baseline in itch-related quality of life at each week of the Double-blind Treatment Period, as assessed by the 5-D Itch Scale total score. Treatment differences between CR845 and placebo at each postbaseline time point will be evaluated using the same MMRM fitted for the secondary efficacy analysis.
- Change from baseline in itch-related quality-of-life at each week of the Double-blind Treatment Period, as assessed by the Skindex-10 Scale total score. Treatment differences between CR845 and placebo at each postbaseline time point will be evaluated using the same MMRM fitted for the secondary efficacy analysis.
- Change from baseline in itch-related quality of life at Week 12 of the Double-blind Treatment Period and at each of the remaining weeks of the Double-blind Treatment Period with respect to each of the 3 domains of the Skindex-10 Scale. Treatment differences with respect to each domain will be evaluated using a model similar to the MMRM fitted for the analysis of the change from baseline in the overall Skindex-10 Scale score (Section 8.7.2).

### **8.8 Safety Analysis**

Analysis of all safety data collected during the Double-blind Phase will be performed on the Double-blind Safety Population. The SAP will provide further detail for the analyses to be applied to each safety parameter, and will also include analyses of safety data collected during the Open-label Extension Phase and during exposure to CR845 during both the Double-blind and Open-label Extension Phases. No statistical hypothesis testing will be carried out and no inferential statistical analysis of the safety parameters will be performed.

The baseline value for all analyses of double-blind safety parameters will be defined as the last value obtained prior to the first dose of double-blind study drug and will include both scheduled and repeat (unscheduled) observations.

---

### 8.8.1 Exposure to Study Drug

For this study, the duration of double-blind treatment for each individual patient may be up to 12 weeks, for a total of approximately 36 doses of study drug administered immediately following each dialysis session. Day 1 of the Double-blind Treatment Period will be defined as the day of administration of the first dose of study drug. The last day of the Double-blind Treatment Period will be defined as the day of the dialysis session immediately following the last injection of study drug.

Exposure and treatment compliance during the Double-blind Treatment Period will be summarized by the following parameters:

- Duration of treatment (days)
- Total number of doses actually received
- Number of missed doses

Duration of treatment (days) = (date of first dialysis after last dose) – (date of first dose) + 1.

If a patient receives additional dialysis during a given week for any reason, an additional dose of CR845 will be administered following dialysis. A maximum of 4 doses per week is allowed. No additional doses will be given for patients receiving an additional unscheduled ultrafiltration treatment. The number of patients getting such an extra treatment will be summarized.

### 8.8.2 Adverse Events

All adverse events, as reported by the site, will be coded using MedDRA to MedDRA SOC and Preferred Term for standardization and summary purposes.

All reported adverse events (whether or not treatment-emergent) will be included in a by-patient adverse event listing. Only TEAEs will be included in summary tables which will present results by treatment group and by study period, as appropriate.

Adverse events that are considered “treatment emergent” relative to the Run-in Period are identified as any adverse event with an onset date after the start of the Run-in Period and up to the first dose of study drug during the Double-blind Period.

Adverse events that are considered “treatment emergent” relative to the Double-blind Period are identified as any adverse event

- with an onset date after the first dose of the double-blind study drug up to the Follow-up Visit or Early Termination Visit (or 7 to 10 days after the last dose if no Early Termination Visit was conducted), whichever is later, for patients who do not enter the Open-label Extension Phase.

- with an onset date after the first dose of the double-blind study drug up to the first dose of open-label drug for patient who continue into the Open-label Extension Phase.

The number and percentage of patients experiencing TEAEs will be summarized by treatment group and by period. A patient will be counted only once in the incidence count for a MedDRA SOC or Preferred Term, although a patient may have multiple occurrences (start and stop) of an event associated with a specific MedDRA Preferred Term or SOC. The most frequent TEAEs ( $\geq 5\%$  of patients in any treatment group) will also be tabulated by SOC and Preferred Term.

The incidence and percentage of patients experiencing treatment-emergent SAEs and TEAEs leading to study discontinuation will be presented by the appropriate MedDRA SOC and Preferred Term. Adverse events that result in death will also be summarized.

Treatment-emergent adverse events will also be summarized by severity for each study period of the Double-blind Phase and by relationship to double-blind study drug for the Double-blind Period. If the severity and/or relationship to the study drug of an adverse event is missing, a worst-case scenario will be assumed (ie, the adverse event will be categorized as “severe” and/or “related” to the study drug). If a patient reports the same TEAE multiple times the event with the worst severity and the strongest relationship to study drug will be tabulated.

For each period of the Double-blind Phase, an overall summary table will be provided, presenting for each treatment group: the number and percentage of patients with an adverse event (both treatment and non-treatment emergent) during that period, a TEAE, serious TEAE, related TEAE, severe TEAE, TEAE leading to dose interruption, and TEAE leading to study drug discontinuation. This table will also include the number of events for each specific Preferred Term.

All adverse events will be listed in chronological order, including patient identifier, age, race, gender, a flag indicating whether the event was treatment-emergent, and all related event status information (start and stop dates, whether the event was ongoing, study day of onset, severity, seriousness, relationship to study medication, action taken with study treatment, and outcome). Separate listings will be generated for SAEs, deaths, and adverse events leading to study drug discontinuation. Additionally, a coding list of Preferred Terms and the verbatim text associated with them will be produced.

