##### **6.5.4.1 Adverse Events**

#### **Definition of Adverse Events**

An adverse event is any untoward medical occurrence in a patient or clinical investigational patient administered a medicinal product and which does not necessarily have to have a causal relationship with this treatment. An adverse event can therefore be any unfavorable and unintended sign (including an abnormal laboratory finding, for example), symptom, or disease temporally associated with the use of a medicinal product, whether or not considered related to the medicinal product.

In this study, adverse events will be captured from the time a patient signs the ICF to the Follow-up Visit and include the following:

- Any new sign, symptom, or disease;
- Any new clinically significant or symptomatic laboratory/diagnostic test abnormality;
- Any clinically significant worsening of laboratory/diagnostic test abnormality;

- 
- Any worsening (ie, clinically significant change in frequency, nature, and/or intensity) of a pre-existing condition.

A pre-existing condition is a condition that is present prior to signing the ICF for the study. Pre-existing conditions, such as illnesses, symptoms, reactions, progression of disease states, and other comorbidities, as well as laboratory/diagnostic test abnormalities, will be documented in the patient's record as medical history.

Signs and symptoms will be reported individually as adverse events (non-serious), unless a medical diagnosis was provided. Medical diagnosis, whenever provided, will be reported rather than individual signs and symptoms.

Any adverse event that satisfies any of the seriousness criteria described below will be reported as an SAE using the SAE Report Form, in addition to documenting in the eCRF. Serious adverse events that occurred up to 30 days after the last dose of study drug need to be documented on an SAE Report Form if they are deemed by the Investigator to be "Related" to study drug.

An SAE that occurred after a period of 30 days from the last dose of study drug must be reported when the investigator becomes aware of it and if there is a possible relationship to the study drug or the conduct of the study.

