#### **6.5.4.2 Structured Safety Evaluation**

A weekly Structured Safety Evaluation will also be used during the Double-Blind Phase to proactively identify and monitor adverse events of special interest.

The Structured Safety Evaluation will be performed once during the Run-in Period and weekly (preferably on Wednesday/Thursday) during the Double-blind Treatment Period. The Structured Safety Evaluation will be performed by qualified study staff using a list of specific signs/symptoms, including mental status change, falls and gait disturbance.

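### The double-blind TEAE definition rests on onset date alone, so an ongoing symptom that begins between consent and first dose and worsens on study drug is not counted

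*Protocol*

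**What the plan says.** Four parts of the protocol bear on this.

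- **TEAE rule (Section 8.8.2).** There are two double-blind rules, one for patients who stop after the Double-blind Phase and one for those who enter the extension. Both require an event "with an onset date after the first dose of the double-blind study drug". Events that begin earlier can be emergent only to the Run-in, defined as "any adverse event with an onset date after the start of the Run-in Period and up to the first dose of study drug". On reporting, the section says "Only TEAEs will be included in summary tables".
- **Adverse event definition (Section 6.5.4.1).** Collection starts at consent: "adverse events will be captured from the time a patient signs the ICF to the Follow-up Visit". The reportable events include "Any worsening (ie, clinically significant change in frequency, nature, and/or intensity) of a pre-existing condition", and the next paragraph fixes the reference point: "A pre-existing condition is a condition that is present prior to signing the ICF for the study". A separate item, with no such limit, covers "Any clinically significant worsening of laboratory/diagnostic test abnormality".
- **Examination and ECG (Sections 6.5.4.3 and 6.5.4.5).** Both state that clinically significant abnormalities or worsening seen after the first dose are reported as TEAEs.
- **Active elicitation (Section 6.5.4.2).** "The Structured Safety Evaluation will be performed once during the Run-in Period and weekly" on treatment. Its purpose is to find adverse events of special interest, and its list includes mental status change, falls and gait disturbance.

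**The concern.** A TEAE definition normally has two arms: events that start after dosing, and events that were already present and get worse. Section 8.8.2 has only the first. The worsening item in Section 6.5.4.1 could stand in for the second, because worsening would then be a new event with its own post-dose onset. But it is anchored to consent, not to first dose, which leaves the time between the two uncovered.

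That time matters here because the protocol looks for symptoms in it. The checklist is run once in the Run-in, so gait or mental-status symptoms found then acquire an onset date before dosing. Dizziness and somnolence are among the events most often reported with CR845 (Sections 4.2.2 and 4.3), and randomization is stratified on falls, confusion and gait conditions (Section 8.3). If study drug aggravated such a symptom, the aggravation is what the double-blind safety tables should show. Randomization balances the symptoms present before dosing. It does not balance any worsening that the drug causes.

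**Working it through.** The plan states no figure to reproduce, and the point depends on no rate or sample size. The check is to apply the written rules to each kind of event.

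**Length of the window.** Section 6.1.1.1 has consent signed at the Screening Visit, which Section 6.1.1 places 7 to 28 days before randomization. The first dose is on Day 1. The window is therefore at most 28 days. It can be shorter, since the Screening Visit may be held within the Run-in.

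**Case by case, for an event that worsens after the first dose:**

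1. *Condition present before consent.* It is pre-existing, so its worsening is a new adverse event with post-dose onset and counts as a double-blind TEAE. Covered.
2. *Symptom starting after consent but before the Run-in.* It is not pre-existing, so the worsening item does not apply. Its onset precedes both the Run-in window and the first dose. It is emergent to no period.
3. *Symptom starting in the Run-in.* It is not pre-existing. It is emergent to the Run-in only, not to the Double-blind Period.
4. *Discrete event that recurs, such as another fall.* The recurrence has its own onset. Covered.
5. *Laboratory or diagnostic abnormality first seen before dosing.* Its worsening is an adverse event in its own right. Covered.
6. *Examination or ECG finding.* Worsening after the first dose is reported as a TEAE. Covered, but narrowly. In the Double-blind Phase, Table 2 schedules the physical examination only at Screening, and the ECG only at Screening and at Day 85 or Early Termination.

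Cases 2 and 3 are the gap.

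**Does record-keeping close it?** The documentation paragraph of Section 6.5.4.1 asks for start and stop dates and a severity for each event. It gives no instruction to start a new record when severity rises. If a site does start one, the onset rule in Section 8.8.2 picks it up. If the site keeps the existing record, the pre-dose onset stands.

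**Where a case 2 or 3 event would appear.** It would be absent from the double-blind tables of TEAEs, severe TEAEs, serious TEAEs and TEAEs leading to discontinuation. It would still be in the by-patient listings, including the separate listings of serious events and of events leading to discontinuation. It might also enter the row of the overall summary table that counts patients with any adverse event, emergent or not, in the period. That row does not show worsening.

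**Internal consistency.** Sections 6.5.4.3 and 6.5.4.5 treat worsening after first dose as treatment-emergent, and Section 8.8.2 does not. Section 8.8 also sets the baseline for double-blind safety parameters at the last value before the first dose, whereas Section 6.5.4.1 sets the reference for worsening at consent.

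**The case against.** The strongest reply has four parts.

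*The SAP may settle it.* Section 8.1 gives the SAP precedence for double-blind analyses, and the SAP is not at hand. This stands in part: the SAP could redefine the TEAE. But this is a rule the protocol states, not a detail it leaves open, and an analysis rule cannot supply a worsening date that sites were never told to record.

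*The event may be reported anyway.* The list in Section 6.5.4.1 is introduced as what adverse events include, so it need not be exhaustive. The general definition is broad enough for a site to report a symptom that becomes severe on drug, and eCRF completion rules are not shown. This also stands in part. That the symptom keeps its earlier onset date is an inference from the documentation rules, not a stated rule. The result then depends on site habit, which is itself a weakness.

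*The information is not lost.* Listings, separate serious-event and discontinuation listings, tabulated reasons for discontinuation (Section 8.6.1) and a summary of fatal events remain. This is correct. What is missing is the comparison by arm in the TEAE tables.

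*The group is small.* Chronic conditions present before consent are covered, eligibility is confirmed again on Day 1, and 28 days is a maximum. This is also correct.

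Two stronger readings are tempting. A reader might infer that a pre-dose event can never become treatment-emergent. The provisions for laboratory, examination and ECG findings, and for pre-consent conditions, contradict that. A reader might also infer that the rule hides a CR845 excess of some given size. The documents give neither the share of patients with a symptom ongoing at Day 1 nor the chance that it worsens, and they show no such excess. Assuming only the first of these would count patients at risk, not patients misclassified.

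**Conclusion.** The point holds in limited form. As written, an ongoing symptom event that begins between consent and first dose and worsens on study drug is not a double-blind TEAE, and Section 8.8.2 disagrees with Sections 6.5.4.3 and 6.5.4.5 on whether worsening counts. The window is up to 28 days per patient. The number of patients affected cannot be estimated from the documents. If study drug did aggravate such symptoms, the double-blind tables would understate the difference between arms; whether it does is unknown.

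The conclusion assumes that sites do not routinely open a new record when severity rises and that the SAP does not already add a worsening clause. If both were in place, only the inconsistency in the protocol text would remain. The change is worth making because the checklist deliberately brings symptoms of special interest into this window, and because a missing worsening date is hard to recover later.

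**What to change.** - **Section 8.8.2:** define a double-blind TEAE as an adverse event that starts after the first double-blind dose, or that starts before it and increases in severity or frequency, or becomes serious, after it. This also brings the section into line with Sections 6.5.4.3 and 6.5.4.5.
- **Section 6.5.4.1:** extend the worsening item to any condition or adverse event present before the first dose, not only before consent, and require a new entry dated at the worsening.
- **SAP:** carry the same definition.

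The cost is a few sentences and an eCRF completion note for sites. TEAE counts may rise slightly in both arms. No change to visits, sample size or the efficacy analyses is needed.

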### **6.3 Removal of Patients from Therapy or Assessment**

#### **6.3.1 Discontinuation of Individual Patients**

A patient may withdraw from the study at any time at his/her own request for any reason without prejudice to future medical care by the physician or at the institution.

A patient may be withdrawn at any time due to the following reasons:

1. At the discretion of the Investigator or the Sponsor for safety, behavioral, compliance, or administrative reasons, including, but not limited to:
  - a. Lost to follow-up;
  - b. Adverse event;
  - c. Lack of therapeutic efficacy;
  - d. Pregnancy;
  - e. Eligibility (Inclusion/exclusion criteria);
  - f. Subject non-compliance;
  - g. Subject withdrew consent.
2. If a patient misses 3 consecutive doses either on Week 11 or Week 12 of the Double-blind Treatment Period (these patients may still be eligible for the Open-label Extension Phase at the discretion of the Investigator in consultation with the Sponsor).
3. If patient misses 6 consecutive doses at any time during the Double-blind Treatment Period (these patients may still be eligible for the Open-label Extension Phase at the discretion of the Investigator in consultation with the Sponsor).
4. At the discretion of the Sponsor/Medical Monitor, if a patient receives a prohibited concomitant medication according to [Table 1](#).

- 
5. Any patient who becomes pregnant during treatment must be withdrawn from the study (see [Section 6.5.4.7](#)).

Whenever possible, withdrawal of a patient from study drug by the Investigator should be discussed with the Medical Monitor before the patient stops study drug.

If study drug is discontinued, regardless of the reason, an Early Termination Visit should be completed at the first dialysis after the last dose of study drug or, if not feasible during that timeframe, as soon as feasible. If at all possible, a Follow-up Visit is to be completed 7-10 days after the Early Termination Visit.

A patient may withdraw consent from continued participation in the study at any time. Although a patient will not be obliged to give a reason for withdrawing prematurely, the Investigator must make a reasonable effort to obtain the reason while fully respecting the patient's rights. The reason(s) for termination and date of stopping study drug must be recorded on the electronic case report form (eCRF) and source documents.

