**Table 2. Schedule of Events: Double-blind Phase (Continued)**

Study Procedures	Screening Period		Double-blind Treatment Period a						Double-blind End of Treatment b / Early Termination	Follow-Up Period (for patients not participating in Open-label Extension Phase ONLY)	
	Screening Visit	Run-in Period	Week 1			Weeks 2 to 12					First Day of Week 13
	Visit Days →	Day -28 to Day -7	Day -7 to Day 1	M/Tu	W/Th	F/Sa	M/Tu	W/Th	F/Sa		
		-28 to -7	-7 to 1	1	3	5	8	10	12	85	85 to 95
							15	17	19		
						22	24	26			
						29 k	31	33			
						36	38	40			
						43	45	47			
						50	52	54			
						57 k	59	61			
						64	66	68			
						71 k	73	75			
						78	80	82			
Safety and efficacy evaluations											
Patient training on PRO worksheets	X h,i	X i	X						X		
Worst Itching Intensity NRS (daily) j		X	Record on an ongoing basis						X		
Skindex-10 Scale, 5-D Itch Scale k			X			X k			X k		
Patient Global Impression of Change									X		
Record number of missed dialysis visits and reason(s)			Record on an ongoing basis								
IV administration of study drug			Record on an ongoing basis								
Inflammatory biomarker samples l			X						X		
Adverse event monitoring	X	X	Record on an ongoing basis						X	X	
Concomitant medications (including antipruritic medications) m			X	Record on an ongoing basis						X	X
Structured Safety Evaluation n		X		X			X				

EoT = End of Treatment; ET = Early Termination; F = Friday; FU = follow-up; IV = intravenous; M = Monday; NRS = numerical rating scale; PRO = patient-reported outcome; Sa = Saturday; Th = Thursday; Tu = Tuesday; W = Wednesday

- 
- a. Each visit during the Double-blind Treatment Period will coincide with the patient's normal dialysis treatments.
  - b. The End-of-Treatment Visit in the Double-blind Phase will be the first dialysis visit following the last dose of study drug (ie, first dialysis on Week 13 [Day 85]), which also corresponds to Day 1 of the Follow-up Period (FU Day 1). Only patients not participating in the Open-label Extension Phase are required to complete the Follow-up Period.
  - c. Medical history will be updated on Day 1 with any changes since the Screening Visit, and inclusion/exclusion criteria will be confirmed prior to randomization. Antipruritic medication will be updated at each dialysis visit during the Run-in Period.

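### An early terminator who attends the Early Termination Visit but has no Follow-up Visit gets a shorter TEAE window (nominally 2-3 days after the last dose) than a patient who attends neither visit

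*Protocol*

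**What the plan says.** Section 8.8.2 of the Protocol defines an event as treatment-emergent in the Double-blind Period, for patients who do not go on to open-label drug, if it arises after the first double-blind dose and "up to the Follow-up Visit or Early Termination Visit (or 7 to 10 days after the last dose if no Early Termination Visit" was conducted. The fallback in brackets, with the tie-break that follows it, reads: "or 7 to 10 days after the last dose if no Early Termination Visit was conducted), whichever is later". For patients who enter the extension, the window closes at the first open-label dose.

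The visit timings are in Section 6.3.1. When study drug is stopped, "an Early Termination Visit should be completed at the first dialysis after the last dose of study drug", or as soon as feasible if that cannot be met. The next visit is not guaranteed: "If at all possible, a Follow-up Visit is to be completed 7-10 days after the Early Termination Visit".

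Section 8.8.2 also decides what the definition controls: "Only TEAEs will be included in summary tables". The same section has all reported events listed by patient, whether or not treatment-emergent, and says that events resulting in death will be summarized.

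**The concern.** The fallback depends on the wrong visit. It is meant to supply an end date when a visit is missing, but it is triggered only by a missing ET Visit. The visit that normally sets the end of the window is Follow-up, and Section 6.3.1 accepts that Follow-up may not happen. For a patient with ET and no Follow-up, the tie-break cannot help, because the ET Visit is the only end date the rule supplies.

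Attending one more visit therefore shortens the window. The patients concerned have stopped study drug early and then died, withdrawn or been lost. A patient who dies after ET can never have a Follow-up Visit, so a fatal event with onset after ET falls outside the window by construction. Whether such an event is treatment-emergent would depend on visit attendance and not on time since the last dose.

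**Working it through.** The Protocol gives no figure to reproduce here. The check applies the Section 8.8.2 rule literally to each pattern of attendance.

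**Step 1: last dose to ET.** Under Table 2, "Each visit during the Double-blind Treatment Period will coincide with the patient's normal dialysis treatments". The visit days run 1, 3, 5, 8, 10, 12 and so on to 82, then 85. Across the 36 dosing days, the gap to the next dialysis is 2 days in 24 cases and 3 days in 12. ET at the first dialysis after the last dose is therefore 2 or 3 days after it.

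**Step 2: ET to Follow-up.** 7-10 days (Section 6.3.1).

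**Step 3: nominal end of window, in days after the last dose.**

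| Attendance | Arithmetic | End of window |
|---|---|---|
| ET and Follow-up | 2 + 7 to 2 + 10; 3 + 7 to 3 + 10 | 9-12 or 10-13 |
| Neither visit | fallback | 7-10 |
| ET, no Follow-up | ET date only | 2 or 3 |

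**Step 4: size of the shortfall.**
- Against the same patient with a Follow-up Visit: the ET-to-Follow-up interval, 7-10 days.
- Against a patient with neither visit: 7 − 2 to 10 − 2 = 5-8 days after a 2-day gap; 7 − 3 to 10 − 3 = 4-7 days after a 3-day gap.

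**Step 5: how many patients with an SAE.** The Protocol gives no rate of early termination or of missed Follow-up, so both are assumptions: 10-20% of 350 patients stop early, and 20-50% of those have no Follow-up Visit.
- Patients with the short window: 0.10 × 350 × 0.20 = 7, up to 0.20 × 350 × 0.50 = 35.
- Phase 2 SAE rates over 8 weeks (Section 4.2.2): CR845 27/129 = 20.9%; placebo 4/45 = 8.9%; all patients 31/174 = 17.8%.
- At a constant rate, 7 lost days at the CR845 rate give 20.9% × 7/56 = 2.6%. Expected patients: 2.6% × 7 = 0.2, up to 2.6% × 35 = 0.9.
- At the all-patient rate: 17.8% × 7/56 = 2.2%, giving 0.2 to 0.8.
- With 10 lost days and the CR845 rate for everyone, the top of the range is 20.9% × 10/56 × 35 = 1.3. With the two arms weighted equally, (20.9% + 8.9%)/2 = 14.9%, and the top is 14.9% × 10/56 × 35 = 0.9.

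The expected count is therefore about one patient or fewer. Early terminators may have a higher rate than the Phase 2 average, but the Protocol gives no figure for that.

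**The case against.** The case for leaving the text alone has several parts.

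- **The rule takes the later date.** A reader might infer that the window closes at whichever visit took place. It does not: every patient with a Follow-up Visit gets the full window. A completer who skips both the extension and Follow-up has had an End-of-Treatment Visit and not an ET Visit, so on a literal reading the fallback applies. This stands, and it confines the problem to patients with ET and no Follow-up.
- **2-3 days is nominal.** ET may be held as soon as feasible. Section 6.3.1 also allows withdrawal after 6 consecutive missed doses, or after 3 in Week 11 or 12. On the Table 2 days, the sixth missed dose falls 14 days after the last dose and the third falls 7 days after. An ET Visit after such a withdrawal gives a window at least that long. This also stands.
- **The events do not vanish.** They remain in the adverse event, SAE and death listings (Section 8.8.2). They may also count in the death summary and in the any-adverse-event row of the overall table, which includes non-treatment-emergent events. The restriction of summary tables to TEAEs leaves both of these unclear. A reader might infer that later events drop out of every output; the text does not support that. A fatal event with onset by the ET Visit also remains a TEAE.
- **Few events would be known.** One subsection of Section 6.5.4.1 records events only until Follow-up or early termination. For a patient truly lost after ET, there would be little to classify. What remains is mainly deaths and SAEs that the site learns of.
- **The ET date is not arbitrary.** Section 8.7.2 says that drug given at the last dialysis of a week is not cleared until the first dialysis of the next. An end date at the next dialysis can be defended, but then it should apply to everyone. The rule gives other patients about a week more.
- **The SAP may settle it.** The SAP is not shown and takes primacy over the Protocol. Choosing one day from a 7-10 day range is an ordinary SAP detail. The condition on the fallback is different: Section 8.8.2 states it outright, so it is not a detail left open.

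**Conclusion.** The gap is real and narrow. As written, Section 8.8.2 gives an early terminator with an ET Visit and no Follow-up Visit a shorter window than a patient with neither visit. An SAE or fatal event with onset after ET is then not treatment-emergent and leaves the TEAE tables. When ET is held on schedule, the shortfall is 7-10 days against a patient with both visits and 4-8 days against a patient with neither.

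The expected volume is small: about 0.2 to 0.9 patients with an SAE at 7 lost days, on assumed rates of early termination and missed Follow-up and a constant Phase 2 SAE rate. The reason to correct it is that a single serious or fatal event can be misclassified by visit attendance. The size of the effect on totals is not the argument.

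Two stronger readings are not supported. A reader might infer a bias between arms, but the Protocol gives no sign that early termination or missed Follow-up will differ by arm, and the numbers are too small to show one. A reader might also see a conflict with the 30-day reporting of related SAEs in Section 6.5.4.1. A TEAE window shorter than a reporting period for related SAEs is a design choice, and tabulating those events separately would be a preference.

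**What to change.** Reword the end of the window in Section 8.8.2, and in the SAP if it repeats the rule. For patients who do not enter the extension, end it at the latest of three dates: the actual Follow-up Visit, the actual ET Visit, and one stated number of days after the last dose. The third date should apply whichever visits took place. The Protocol's own upper figure for the fallback is 10 days; using it would also replace the present range by a single cut-off. For extension entrants, keep the cut at the first open-label dose.

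It would help to add a few words on whether the summary of events resulting in death is limited to treatment-emergent events.

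The cost is one sentence and a small programming change, with no new data and no change to visits or patient care. TEAE counts may rise slightly.
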